### **9.1.3. Cosmetic Change(s)**

Subjects who developed AEs during the study with one of the following preferred terms will be included in the cosmetic change summary:

- Blepharal pigmentation
- Eyelash changes
- Eyelash hyperpigmentation

- Eyelash thickening
- Growth of eyelashes
- Lid sulcus deepened
- Trichiasis
- Iris hyperpigmentation

Other preferred terms might be added upon review of the AE data before database lock.

Cosmetic change(s) start time (in terms of study day) will be summarized using mean, standard deviation, median, minimum, and maximum by study eye and fellow eye separately. To allow for the computation of simple descriptive statistics, only subjects who develop cosmetic change(s) during the study will be used for the cosmetic change start time summary.

The aforementioned summaries will be performed at the eye level. All cosmetic change AEs will be provided in a listing.

## **9.2. Best-Corrected Visual Acuity**

BCVA (logMAR scores) and changes from baseline will be summarized by treatment, analysis visit, and study period (double masked and open-label) for study eyes and fellow eyes, separately. In addition, any change (worsening or improvement) of  $\geq 0.2$  LogMAR (2 lines) from baseline will be summarized and listed.

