12. ASSESSMENT OF SAFETY

12.1. Adverse Events and Serious Adverse Events

12.1.1. Definition of Adverse Events

An adverse event (AE) is any untoward medical occurrence in a clinical trial subject. An AE does not necessarily have a causal relationship with the study medication. For this study, the investigational products are DE-117, DE-117 vehicle and Timolol. Regardless of relationship to the study medication, an AE can be a clinically relevant unintended sign (including an abnormal laboratory finding), symptom, or disease.

Any significant change in a subject's condition from the time that written informed consent is obtained, regardless of causality, is to be considered an AE. A clinically significant worsening in severity, intensity, or frequency of a pre-existing condition may indicate an AE.

An elective surgical procedure scheduled or planned prior to study entry that does not require an overnight hospitalization is not considered an AE, and the underlying diagnosis for the procedure should be captured in the medical history as a pre-existing condition. The surgical procedure should also include the term "elective" in all reports. An elective or planned hospitalization must be reported as an SAE.

The lack of efficacy of the study medication for the condition being investigated is not considered an AE unless a clinically significant change is assessed by the Investigator.

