12.2. Safety Parameters

In addition to observed values, changes from baseline will be evaluated at relevant post baseline visits. For a safety outcome measure, the baseline value will be the last observation of that outcome measure prior to the first dose of study medication.

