### 3. STUDY DESIGN

#### 3.1. General Study Design

[figure not shown]
This is a phase 3, randomized, double-masked, active-controlled, parallel-group, multi-center study. Subjects diagnosed with glaucoma or OHT who meet eligibility criteria at Visit 1 (Screening) will discontinue their current topical IOP-lowering medication(s), if any. After completing the required washout period, subjects will return for Visit 2 (Baseline, Day 1). Subjects who meet all eligibility criteria at baseline will be randomized to receive double-masked treatment for 3 months.

Approximately 400 eligible adults and up to 30 eligible pediatric subjects with glaucoma or OHT were planned to be randomized in a 1:1 ratio to receive either:

- **Test regimen – DE-117 0.002% QD:** DE-117 0.002% QD (one drop/eye each day at 20:00) and vehicle QD (one drop/eye each day at 08:00) for the three-month duration of the double-masked treatment period.
- **Control regimen – Timolol 0.5% BID:** Timolol 0.5% BID (one drop/eye each day at 20:00 and one drop/eye each day at 08:00) for the three-month duration of the double-masked treatment period.

At the end of the double-masked period, all adult subjects will enter the open-label period and receive DE-117 Ophthalmic Solution 0.002% for an additional 9 months ([Figure 1](#)).

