#### 4.2.2. Baseline Score

The *baseline score* is the observed measurement at Visit 2 (Baseline). If a baseline score is missing, the last observed measurement or derived score prior to the first dose of study medication will be used to impute the baseline score.

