### 4.2.3. Change and Percent Change from Baseline

The change and the percent change from baseline in a measure at a post-baseline visit will be derived as:

- Change = (Score at the Post-Baseline Visit) – (Baseline Score)
- Percent Change from Baseline =  $100 \times \text{Change} / (\text{Baseline Score})$

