### 9.1. Adverse Events

AEs, SAEs, SARs, serious SARs, and significant AEs (AEs leading to study drug discontinuation and AEs leading to death) will be tabulated by type of AEs by treatment arm using actual treatment received for all AEs, ocular AEs, and non-ocular AEs separately.

Besides the overall AE summary, AEs, SAEs, SARs, serious SARs will be tabulated by SOC and preferred term for all AEs, ocular AEs, and non-ocular AEs separately. A subject who experienced multiple AEs within a SOC or preferred term will be counted only once for that SOC or preferred term. Non-serious AEs (including number of events) and ESIs will also be summarized by SOC and preferred term.

All the AE summaries will be performed for double-masked, open-label, and entire study periods separately. For double-masked period summaries, overall AE summary, summary of AE by SOC and PT, SAEs, SARs, and serious SARs will also be tabulated on pediatric subjects separately. For open-label and entire study period summaries, tabulations by treatment received during double-masked period will be provided as well as overall summary for subjects exposed to DE-117. So, for subjects who exposed to the Timolol arm during the double-masked period, their AE summaries under the Overall DE-117 column will be those AEs that started during the open-label treatment period.

AEs, SAEs, SARs, serious SARs, ocular AEs, AEs leading to death, AEs leading to study drug discontinuation, non-TEAEs, and ESIs, if any, will be listed separately.

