## **9.3. Slit-lamp Biomicroscopy**

For each biomicroscopy parameter, frequency and percentage of rating scores will be summarized by treatment, analysis visit and study period (double masked and open-label) for study eyes and fellow eyes, separately. In addition, any clinically significant worsening (increase) from baseline will be summarized and listed.

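### Open-label BCVA and slit-lamp change in former Timolol subjects is measured only from Visit 2, so it mixes change on Timolol with change on DE-117

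*SAP*

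**What the plan says.** **Baseline.** SAP 4.2.2 defines one baseline score, which "is the observed measurement at Visit 2 (Baseline" visit; a missing value is replaced by the latest one taken before dosing began. SAP 4.2.3 gives one formula, "Change = (Score at the Post-Baseline Visit) – (Baseline Score", with no version for the open-label period. For safety measures, Protocol 12.2 says that "the baseline value will be the last observation of that outcome measure prior to the first dose of study medication". Protocol 12.1.1 adds: "For this study, the investigational products are DE-117, DE-117 vehicle and Timolol".

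**Switch at Month 3.** Under SAP 3.1, "all adult subjects will enter the open-label period and receive DE-117 Ophthalmic Solution 0.002% for an additional 9 months". This includes the adults who were randomized to Timolol.

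**Examination summaries.** SAP 9.2 states: "BCVA (logMAR scores) and changes from baseline will be summarized by treatment, analysis visit, and study period (double masked and open-label". It also summarizes and lists changes of 0.2 logMAR or more in either direction. SAP 9.3 tabulates slit-lamp grades by visit and period, and adds that "any clinically significant worsening (increase) from baseline will be summarized and listed".

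**How other data are split.** For subjects who took Timolol in the double-masked period, SAP 9.1 says that "their AE summaries under the Overall DE-117 column will be those AEs that started during the open-label treatment period". SAP 7.7 removes Timolol days from their DE-117 exposure.

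**The concern.** The Month 12 analysis is meant to describe long-term safety of DE-117 (Protocol 14.2). About half of the adults who can enter the open-label period first take DE-117 at Month 3. For them, a change from Visit 2 to Month 6, 9 or 12 is the sum of what happened on Timolol and what happened on DE-117.

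Two kinds of error follow. A Timolol-period change that persists is flagged again at open-label visits. A loss on DE-117 that undoes an earlier gain nets to zero at the later visit. The rule is therefore not simply conservative: it can overstate or understate a DE-117 finding.

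The same baseline feeds the macular edema summary in SAP 9.1.2, which reports BCVA change from baseline at onset, at resolution and at the last visit. Macular edema is an event of special interest.

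**Working it through.** The plan states no figure on this point, so there is nothing to reproduce. The check traces the definition and then applies it to example subjects.

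**Step 1. Which baseline applies?** SAP 4.2.2 fixes Visit 2. Protocol 12.2 fixes a value before any study medication, and Protocol 12.1.1 counts Timolol among the investigational products. Both routes put the baseline of a Timolol-arm subject before Timolol. Neither document defines a Month 3 or open-label reference.

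**Step 2. What the change score contains.** For a former Timolol subject at Month 6:

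Month 6 − Visit 2 = (Month 3 − Visit 2) + (Month 6 − Month 3)

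The first bracket is change on Timolol and the second is change on DE-117. The SAP reports only the sum.

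**Step 3. Apply the 0.2 logMAR rule.** The values below are illustrative. A positive change is a loss of acuity.

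| Visit 2 / Month 3 / Month 6 | Month 6 from Visit 2 | Flag at Month 6 | Month 6 from Month 3 | Flag |
|---|---|---|---|---|
| 0.10 / 0.30 / 0.30 | 0.30 − 0.10 = +0.20 | yes | 0.30 − 0.30 = 0.00 | no |
| 0.10 / 0.20 / 0.30 | 0.30 − 0.10 = +0.20 | yes | 0.30 − 0.20 = +0.10 | no |
| 0.30 / 0.10 / 0.30 | 0.30 − 0.30 = 0.00 | no | 0.30 − 0.10 = +0.20 | yes |

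In the first row nothing changed on DE-117, yet the subject is flagged. In the second, half of the flagged change arose on Timolol. In the third, a two-line loss on DE-117 is not flagged at Month 6. The slit-lamp flag follows the same logic, but only for worsening judged clinically significant.

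**Step 4. Size.** The documents give no rate of persistent change on Timolol. Let p be the assumed share of former Timolol subjects with a persisting flagged change at Month 3. The planned arm size of 200 (Protocol 14.3.1) is the most that can enter.

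- Full retention: 200 × 1% = 2 and 200 × 5% = 10 subjects.
- 80% retention (also assumed): 160 × 1% = 1.6 and 160 × 5% = 8 subjects.
- If both arms were pooled with equal retention, this is p/2 of the pooled group: 0.5% to 2.5%.

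**Step 5. Is the alternative reference available?** Yes. At Visit 5, BCVA and biomicroscopy are done before the 08:00 IOP (Protocol 7.4.6), as at Visits 6 to 8. The first open-label dose is that evening (Protocol 7.1), and SAP Table 3 already defines an open-label treatment start date.

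**The case against.** **The attribution to DE-117 is not stated.** A reader might infer that the plan pools former Timolol subjects into one DE-117 column and so charges the comparator's three months to DE-117. The documents do not settle this. SAP 9 groups safety measures by the drug actually taken, which points to DE-117 for everyone in the open-label period. The open-label layout for adverse events in SAP 9.1 uses the double-masked arms plus an overall column. Sections 9.2 and 9.3 do not say which meaning of treatment applies. This stands, and it is itself something to clarify. Showing the arms separately would still leave Timolol-period change inside the open-label flag counts.

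**Existing outputs expose part of the carry-over.** Results are shown by visit, and every BCVA change of at least 0.2 logMAR is listed, gains included. A persistent Timolol-period loss would appear at Month 3 as well as later. The 0.30 / 0.10 / 0.30 subject would be listed at Month 3 as improved. The information can be recovered by reading visit tables and listings together, but not from the later counts alone.

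**The slit-lamp effect is narrow.** The main table in SAP 9.3 gives grades by visit and does not depend on a baseline. Only the flag for clinically significant worsening does. This stands.

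**The adverse event tables do not contradict the examination tables.** Events are assigned by onset, while examinations are compared with a pre-treatment value. A reader might see an inconsistency, but these are different measures. What is missing is a counterpart for the examinations.

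**Visit 2 is a defensible reference.** A Visit 5 value is taken on an active drug. The package insert in Protocol Appendix E lists keratitis, dry eyes and visual disturbances, so recovery after stopping Timolol could look like improvement on DE-117. This is a good reason to add the Visit 5 reference rather than substitute it.

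**Conclusion.** The point holds as a gap in attribution. For former Timolol subjects, the open-label BCVA change flag and the slit-lamp worsening flag cannot separate change on DE-117 from change on Timolol, and the error can go in either direction. It arises only when a Timolol-period change persists to, or contributes to, an open-label value.

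The size is unknown. The 2 to 10 subjects rest on an assumed 1% to 5% and on all 200 Timolol subjects continuing. The share of a combined group also assumes pooling that the SAP does not state. A reader might infer that carried-over findings could match or outnumber new ones; the documents give no rate for either, so they do not support this.

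These summaries are descriptive, and SAP 6 rules out testing of safety measures. Power, Type I error and all efficacy results are unaffected. Change from Visit 2 remains valid as a whole-study summary. This is a cheap improvement to the long-term safety reading, not a flaw that endangers the trial's conclusions.

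**What to change.** 1. In SAP 4.2.2, define an additional open-label baseline for adults randomized to Timolol: the last value before the first open-label DE-117 dose, normally Visit 5.
2. In SAP 9.2 and 9.3, report open-label BCVA change, the 0.2 logMAR flag and the slit-lamp worsening flag against this baseline, alongside the Visit 2 results.
3. State what treatment means in the open-label examination tables. Show them by double-masked arm plus an overall DE-117 column, as in SAP 9.1, and use the open-label baseline for former Timolol subjects in the overall column.

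Subjects randomized to DE-117 keep Visit 2 throughout, as does the double-masked period.

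**Cost.** One derived baseline flag, an extra column, and a footnote saying that the open-label baseline of former Timolol subjects was measured on Timolol and that the overall column mixes two reference visits. No new data are needed.

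**What it does not cover.** Vital signs (SAP 9.6) share the same baseline. Eyelid, eyelash and iris ratings (SAP 9.5) are judged against Visit 2 photographs, so they cannot be re-referenced by a derivation alone; a footnote is the practical remedy there.

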## **9.3. Slit-lamp Biomicroscopy**

For each biomicroscopy parameter, frequency and percentage of rating scores will be summarized by treatment, analysis visit and study period (double masked and open-label) for study eyes and fellow eyes, separately. In addition, any clinically significant worsening (increase) from baseline will be summarized and listed.

## **9.4. Ophthalmoscopy**

Cup-to-disc ratio will be summarized with n, mean, standard deviation, median, minimum and maximum by treatment, analysis visit, and study period (double masked and open-label) for study eyes and fellow eyes separately. In addition, subjects with at least 0.2 increase in cup/disc ratio from baseline will be listed.

Glaucomatous optic nerve findings will be assessed as 0 = none, 1 = mild, 2 = moderate, or 3 = severe. Frequency and percentage of rating scores will be summarized by treatment and analysis visit for study eyes and fellow eyes, separately. In addition, subjects with any worsening (increase) of  $\geq 2$  units from baseline will be listed.

Retina/Macula/Choroid and vitreous will be assessed as normal or abnormal. Shift from baseline at Month 3 will be summarized by treatment on study eyes and fellow eyes separately. In addition, subjects with change from baseline from normal to abnormal in these parameters will be listed.

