11. History of keratorefractive surgery (e.g., RK, PRK, LASIK) in either eye.
12. Allergy, hypersensitivity or contraindications to EP2 receptor agonists, beta-blockers, benzalkonium chloride (BAK) or any other components of the study medications, or other study related procedures/medications. This also includes subjects with a history or presence of contraindications to beta-blocker therapy, such as chronic obstructive pulmonary disease (e.g., chronic bronchitis, emphysema), bronchial asthma, second or third degree atrioventricular block, uncontrolled congestive heart failure.

Diseases

13. Presence of advanced glaucoma (e.g., visual field mean deviation worse than -12 dB) in either eye.
14. Presence of any corneal abnormality or other conditions interfering with or preventing reliable Goldmann applanation tonometry (e.g. Fuch's dystrophy or significant corneal surface abnormality) in either eye.
15. Presence of any active severe external ocular disease, inflammation, or infection of the eye and/or eyelids in either eye.
16. Presence or history of macular edema or known risk factors for macular edema in either eye.
17. History of severe ocular trauma in either eye.
18. History of iritis and/or uveitis in either eye.
19. History of retinal detachment, proliferative diabetic retinopathy, or any retinal disease that may be progressive during the time course of the study in either eye.
20. Presence or history of any disease or condition that in the opinion of the study Investigator may put the subject at significant risk, may confound study results, or may interfere significantly with the subject's participation in the study (e.g., recurrent corneal erosion syndrome, uncontrolled cardiovascular disease etc.).
21. Any decision by the Investigator or Medical Monitor to terminate a subject in screening or declare any subject ineligible for any sound medical reason.

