21.3.12. Ophthalmoscopy (Fundus) Examination

The ophthalmoscopy (fundus) examination will be performed for each eye at Visit 1, Visit 2, Visit 5, and Visit 8 Study Exit/Early Termination, and graded as described below. The examination will be performed with pupil dilated at Visit 1 and Visit 8/Study Exit. Please dilate pupil and perform after all other ocular procedures have been completed. Cup to disc ratio and abnormality in retina, macula, choroid, and vitreous will also be evaluated.

Glaucomatous Optic Nerve Findings

The optic nerve will be evaluated using a 4-point scale (0-3 scale).

None (0) = No damage

Mild (1) = Optic nerve damage, secondary to glaucoma including any rim loss (sloping or thinning)

Moderate (2) = Optic nerve damage, including cupping to disc margin at one or more points

Severe (3) = Optic nerve damage, nearly total cupping, only nasal rim or less present

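### The SAP's optic-nerve worsening listing cannot record a change from Moderate (2) to Severe (3)

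*SAP*

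**What the plan says.** Protocol 21.3.12 sets the scale: "The optic nerve will be evaluated using a 4-point scale (0-3 scale". The two upper grades are "Moderate (2) = Optic nerve damage, including cupping to disc margin at one or more points" and "Severe (3) = Optic nerve damage, nearly total cupping, only nasal rim or less present". SAP 9.4 uses the same four grades: "Glaucomatous optic nerve findings will be assessed as 0 = none, 1 = mild, 2 = moderate, or 3 = severe".

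For this grade SAP 9.4 plans two outputs. One is the frequency and percentage of each grade by treatment and analysis visit, with study and fellow eyes shown separately. The other is a listing: "subjects with any worsening (increase) of $\geq 2$ units from baseline will be listed". A separate listing covers the cup/disc ratio: "subjects with at least 0.2 increase in cup/disc ratio from baseline will be listed".

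On entry, Protocol 8.2 excludes adults on this ground: "Presence of advanced glaucoma (e.g., visual field mean deviation worse than -12 dB) in either eye". The pediatric criterion in Protocol 8.4 also excludes advanced glaucoma, without an example. Neither sets a limit on the optic-nerve grade or the cup/disc ratio, and SAP 7.2 provides for all four grades in the baseline table.

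Protocol 12.2.1 names the glaucomatous optic nerve as the ophthalmoscopy variable. Protocol 14.8 says that changes from baseline in the parameters of that section will be summarized by treatment.

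**The concern.** A fixed 2-unit threshold on a scale that stops at 3 can be met only from grades 0 and 1. The step into the worst grade from the one below it is out of reach of the rule by construction. A reader of the study report who finds no Moderate-to-Severe case in the listing could take this as evidence that none occurred, although the rule could not have shown one.

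No scheduled functional test backs up the disc grade, because the visual field is examined only at screening (SAP Table 1 and Table 2). The SAP is also less strict with other structures. It gives retina/macula/choroid and vitreous a shift summary and lists any change from normal to abnormal (9.4). It lists any clinically significant biomicroscopy worsening (9.3) and any eyelid sulcus change (9.5). It gives no reason for a 2-unit threshold on the optic nerve.

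**Working it through.** **Inputs.** Grades 0 to 3 (Protocol 21.3.12, SAP 9.4); listing threshold of at least 2 units (SAP 9.4); cup/disc threshold of at least 0.2 (SAP 9.4). The documents state neither the range nor the recording step of the cup/disc ratio. I assume 0 to 1.0 in steps of 0.1. The plan gives no figure of its own to reproduce here.

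**Step 1: room to worsen.** Largest possible increase = 3 − baseline grade.

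| Baseline grade | Largest increase | Can reach +2? |
|---|---|---|
| 0 | 3 − 0 = 3 | yes |
| 1 | 3 − 1 = 2 | yes |
| 2 | 3 − 2 = 1 | no |
| 3 | 3 − 3 = 0 | no (already at the top) |

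**Step 2: transitions.** There are 3 + 2 + 1 = 6 possible worsening transitions. The rule lists 0→2 (+2), 0→3 (+3) and 1→3 (+2). It omits 0→1, 1→2 and 2→3 (each +1). It therefore lists 3 of 6, and none that starts at grade 2.

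**Step 3: what the grade frequencies show.** They are marginal counts. Suppose one eye goes from 2 to 3 and another is regraded from 3 to 2. The counts at baseline and at the visit are then the same: one eye at 2 and one at 3. If the count at grade 3 does rise, the table does not say whether the eye came from 0, 1 or 2, or whose eye it was.

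**Step 4: the cup/disc listing.** A rise of 0.2 needs 1.0 − baseline ≥ 0.2, so baseline ≤ 0.8. On the assumed 0.1 steps, 9 of the 11 possible baseline values can be listed. The exceptions are 0.9 (room 0.1) and 1.0 (room 0). A grade 2 eye with a ratio of 0.8 or less is listed here if the ratio rises by 0.2. It is not listed if it moves to Severe with a smaller rise, for example 0.8 to 0.9.

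**Step 5: Protocol against SAP.** Protocol 14.8 with 12.2.1 calls for a change-from-baseline summary of the optic-nerve variable by treatment. SAP 9.4 plans none. SAP Section 10 records three departures from the protocol (the Full Analysis Set definition, an added key secondary endpoint and the removal of LOCF); this is not among them.

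**The case against.** A two-step threshold is a legitimate way to keep grader noise out of a listing based on a subjective ordinal grade. That stands for baseline grades 0 and 1, and it is why the omission of 0→1 and 1→2 is not counted here as a fault. It does not help at grade 2, where no two-step change exists.

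A reader might infer that a Moderate-to-Severe change would escape every output. The documents do not support that. Protocol 12.1.1 allows a clinically significant worsening of a pre-existing condition to be an adverse event, and SAP 9.1 lists adverse events. Protocol 8.5 names progressive disease as a reason for withdrawal, and SAP 7.1 tabulates discontinuations by primary reason. These routes depend on the investigator's judgement and do not use the graded data, but they exist.

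A reader might also infer that the cup/disc rule has the same ceiling. It does not: it is a different measure and, on the assumed range, is out of reach only above a baseline of 0.8. Grade 2 is defined by cupping to the margin at one point or more. That can be focal, so grade 2 does not imply a ratio above 0.8.

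It can also be said that this is a listing without inference (SAP 6 rules out statistical testing of safety measures) and that a shift table could be produced at any time from the collected grades. Both are true. They limit the importance of the point but are no reason to leave the table unplanned.

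**Conclusion.** The point holds for the optic-nerve listing in SAP 9.4: an eye at Moderate (2) cannot put its subject on that listing by progressing to Severe (3), and such eyes are eligible. This part rests only on the scale and the threshold and needs no assumption. The grade frequencies do not replace the missing within-eye view, and the SAP leaves out, without recording it, a change-from-baseline summary that the protocol announces. The cup/disc listing is a partial backstop; its ceiling of 0.8 depends on the assumed 0 to 1.0 range.

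The consequence is confined to descriptive safety output. No efficacy result, error rate, analysis population or sample size changes. The documents give no distribution of baseline grades, so the number of eyes outside the rule cannot be computed, and any count would be a guess.

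**What to change.** In SAP 9.4:

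1. List any subject whose optic-nerve grade shifts to Severe (3) from a lower baseline, in addition to any worsening of at least 2 units. This covers 0→2, 0→3, 1→3 and 2→3, which is 4 of the 6 transitions.
2. Add a baseline-by-visit shift table for the grade by treatment, for study eyes and fellow eyes separately. It shows the remaining one-step changes (0→1 and 1→2) and delivers the summary announced in Protocol 14.8.

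The cost is a change of SAP wording and one table from data already collected. The listing becomes slightly longer and takes in some grader noise. One caution should go into the table footnote. Baseline is Visit 2 (SAP 4.2.2), where the adult examination is scheduled without dilation, whereas Visit 8 is scheduled with it (Protocol 21.3.12, SAP Table 1). A one-step shift at Month 12 in adults may therefore partly reflect technique. For the same reason I would not list every one-unit worsening. Nor would I add a lower cup/disc cut-off for high baselines, since the documents do not state the recording step of the ratio.
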